# **Objectives**

• To describe the relationship between stroke-related sarcopenia with loss of connectivity in the brain

SINONIMS Protocol V1.0 24.09.18 (Amendment 1.1 01/11/19) (Amendment 1.2 17/08/20) (Amendment 1.3 05/01/21) (Amendment 1.4 18/05/2021) IRAS ID 249942 Page 7 of 24

- To describe the relative strengths of correlation of individual muscle and brain imaging biomarkers to motor outcome (as determined by lower limb Fugl-Meyer score, lower limb motor NIHSS and dynamometry measurement) compared to that of a combination of imaging biomarkers to motor outcome
- To develop a predictive model of motor outcome at 3 months based on brain and muscle biomarkers obtained 1-4 weeks after stroke
- To establish the feasibility of obtaining simultaneous brain and muscle MRI imaging relatively early after stroke by description of recruitment rate, drop-out rate and rate of incomplete and sub-optimal imaging
- To obtain data to inform the design and sample size required for a blinded observational study to confirm the operational characteristics of an algorithm using baseline advanced MRI biomarkers of neurological injury and sarcopenia to predict motor outcome.

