## Planned advanced MRI imaging

A 3 Tesla MRI study will take place in the Magnetic Resonance Imaging Centre in Centre for Aging and Vitality (CAV) in Newcastle University or in the Neuroradiology department, Royal Victoria Infirmary, Newcastle-upon-Tyne. The research team will liaise with the participant (or the relevant clinical team if still in hospital) and the MRI team to pre-book an appointment. The study will take approximately 45-50 min. Travel and parking costs for the participants will be re-imbursed from the study budget.

The CTO/member of the clinical team at the recruiting site will undertake an initial MRI safety screening (for absolute contraindications e.g. cardiac pacemaker) before obtaining permission to pass on the patient's details to the research associate. A member of the research team will subsequently undertake additional screening for MRI safety at the time of booking the MRI study. A member of the MRI team will undertake a final MRI safety screening with the patient on the day immediately before the study is undertaken. Any instance of study being cancelled due to MRI safety concern will be documented and reported alongside study results.

The following MRI sequences will be performed (Appendix 7):

1. Brain imaging: Structural - 3D volume T1; Functional imaging: DTI (approx. 15 min).

SINONIMS Protocol V1.0 24.09.18 (Amendment 1.1 01/11/19) (Amendment 1.2 17/08/20) (Amendment 1.3 05/01/21) (Amendment 1.4 18/05/2021) IRAS ID 249942 Page 11 of 24

2. Muscle imaging: 3D volume T1, STIR, 3 point Dixon or equivalent, MR spectroscopy of the thigh muscles (approx. 25-30 min).

The images will be transferred to a workstation for review by an observer who will be blinded to the clinical status of the patient. Following assessments will be made on the structural brain imaging: lesion location, lesion side, lesion number, lesion volume, anatomical structures involved, vascular territory involved, any other pathology.

The following quantitative assessments will be made from the functional brain imaging sequences: DTI imaging – a region of interest will be drawn on the pyramidal tracts at the level of mid-brain and internal capsule and the following parameter will be measured: FA, relative FA (i.e. FA ratio between normal and abnormal sides) and axial, radial and mean diffusivity.

The following assessments will be made from the muscle MRI:

- a) Muscle volume, based on a 6 point scale described by Mercuri et al (10)

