## Image data

The following data will be extracted from the cranial MRI studies:

- Site of infarction location will be anatomically classified as frontal, parietal, temporal, occipital, basal ganglia; it will also be classified along vascular territories e.g. middle cerebral artery, anterior cerebral artery or posterior cerebral artery, etc
- Side of infarction
- Infarct volume region of interest (ROI) will be placed on the affected region and volume will be measured using validated software
- Cross-sectional DTI measurements axial, radial and mean diffusivity (AD, RD and MD), fractional anisotropy (FA) (ROIs will be placed in the cortico-spinal tracts on both sides at the levels of corona radiata, internal capsule and cerebral peduncle).
- Whole tract DTI measurement 3D Tractographic analysis of the whole cortico-spinal tract on both sides will be made with measurements of whole tract volume, MD and FA.

The following data will be extracted from the muscle MRI studies:

• Muscle volume – this will be performed on the T1 volume data based on a 6 point scale described by Mercuri et al. The volume of the whole thigh and that of the largest thigh muscle (vastus lateralis) will be measured.

SINONIMS Protocol V1.0 24.09.18 (Amendment 1.1 01/11/19) (Amendment 1.2 17/08/20) (Amendment 1.3 05/01/21) (Amendment 1.4 18/05/2021) IRAS ID 249942 Page 12 of 24

- Fat fraction analysis this will be done using the fat only images obtained from 3 point Dixon method.
- Intra-myocellular lipid content MR spectroscopy will be performed on the Vastus Lateralis muscle on both sides. Intra-myocellular lipid fraction will be obtained by interrogating the two lipid peaks seen on the MR spectrum.
- Muscle oedema this will be obtained from the STIR sequence based on a 4 point scale (absent, mild, moderate, severe).

All measurements will be made in the affected and normal sides and a ratio of parameters between the two sides will be calculated.

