# Data analysis

In order to effectively explore this research question, two hypotheses are proposed:

*Hypothesis A*: Sarcopenia and loss of motor impairment will be most pronounced in those patients whose ischaemic stroke causes greatest damage to the cortico-spinal (CS) tract and motor pathways as determined by advanced neuroimaging.

*Hypothesis B*: A combination of imaging biomarkers of loss of connectivity in brain and sarcopenia will increase the ability to predict motor outcome in stroke when compared to individual biomarkers alone.

In line with the study hypotheses the following broad categories of analyses will be undertaken.

SINONIMS Protocol V1.0 24.09.18 (Amendment 1.1 01/11/19) (Amendment 1.2 17/08/20) (Amendment 1.3 05/01/21) (Amendment 1.4 18/05/2021) IRAS ID 249942 Page 13 of 24

*Analysis* A: Degree of sarcopenia (as determined by study of muscle volume, fat fraction and oedema on MRI) will be used as a covariate in a regression analysis between motor outcome (lower limb Fugl-Meyer score) and neuroimaging assessment of CS tract integrity (fractional anisotropy or FA as determined from diffusion tensor imaging or DTI).

*Analysis B*: Correlation of a combined biomarker of brain connectivity and sarcopenia versus motor outcome (as determined by lower limb Fugl-Meyer score) will be stronger than correlation between individual biomarkers and motor outcome.

The following individual statistical analyses will be performed:

- Correlation between cortico-spinal tract (CST) DTI data (AD, RD, MD and FA of cross sectional data and MD and FA of 3D tractographic data) and muscle MRI data (volume, fat fraction, intra-myocellular lipid fraction and muscle oedema)
- Correlation between CST DTI data and lower limb Fugl-Meyer score, motor NIHSS and dynamometry measurement at 3 months
- Correlation between CST DTI data and change in Fugl-Meyer score, motor NIHSS and dynamometry measurement between baseline and 3 months
- Correlation between muscle MRI data and Fugl-Meyer, motor NIHSS and dynamometry measurement score at 3 months
- Correlation between muscle MRI data and change in Fugl-Meyer score, motor NIHSS and dynamometry measurement between baseline and 3 months
- Correlation between combined CST DTI/muscle MRI data and lower limb Fugl-Meyer score at 3 months
- Correlation between combined CST DTI/muscle MRI data and change in lower limb Fugl-Meyer score between baseline and 3 months

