- Multi-variate regression analysis of muscle and cranial DTI data and lower limb Fugl-Meyer scores.

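### Infarct volume is measured on the structural scan but used in none of the listed analyses, so they cannot show whether corticospinal DTI tells more than infarct size

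*Protocol*

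**What the plan says.** Two sections call for infarct size. Planned advanced MRI imaging states: "Following assessments will be made on the structural brain imaging: lesion location, lesion side, lesion number, lesion volume". Image data repeats it: "Infarct volume region of interest (ROI) will be placed on the affected region and volume will be measured using validated software". Both are separate from the DTI measurements.

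Data analysis then sets out two broad analyses and eight individual ones.

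- Analysis A regresses lower limb Fugl-Meyer score on FA, and its one stated adjustment is "Degree of sarcopenia (as determined by study of muscle volume, fat fraction and oedema on MRI) will be used as a covariate".
- Analysis B compares a combined brain and muscle biomarker with individual biomarkers.
- The individual analyses correlate corticospinal DTI data, muscle MRI data or their combination with motor outcome, for example "Correlation between CST DTI data and lower limb Fugl-Meyer score, motor NIHSS and dynamometry measurement at 3 months".
- The last entry is "Multi-variate regression analysis of muscle and cranial DTI data and lower limb Fugl-Meyer scores".

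DTI data are defined there as axial, radial and mean diffusivity and FA, so infarct volume does not come in under that label. Among the Objectives is "To describe the relative strengths of correlation of individual muscle and brain imaging biomarkers to motor outcome", and another objective is a predictive model built on brain and muscle biomarkers in general terms.

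**The concern.** A larger infarct can plausibly both lower tract FA and worsen leg function. If so, FA and outcome will correlate even where FA adds nothing to infarct size. None of the listed analyses distinguishes that case from one in which tract damage matters at a given infarct size.

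The protocol's own questions make the distinction relevant. Hypothesis A is about damage to the corticospinal tract and motor pathways, and overall infarct size is an obvious rival explanation. The Summary asks whether advanced MRI can predict recovery, and infarct volume from the structural scan is the natural conventional-MRI comparator. The objective on individual biomarkers compares brain imaging measures, yet the listed analyses leave out one that is already measured. The final objective uses the results to plan a study of an algorithm based on advanced MRI. Knowing whether DTI adds to a simpler measure from the same session would help that planning.

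**Working it through.** **Check of the text.** Infarct or lesion volume appears in 0 of the 2 broad analyses and 0 of the 8 individual analyses. The only covariate named is sarcopenia, and the final regression names muscle and DTI data only.

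**No stated figure to reproduce.** Case ascertainment, consent and recruitment says that no formal sample size calculation was done. The protocol gives no significance level, power or correlation.

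**Inputs.** n = 30 attending MRI is from the protocol. Assumed: n = 25 as an illustration of incomplete data, a two-sided 5% test, normally distributed variables, and the correlations below (absolute values).

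**Formulas.** Let a be the FA-volume correlation, b the volume-outcome correlation and r the FA-outcome correlation.

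- Partial correlation of FA and outcome given volume: (r − ab) / √[(1 − a²)(1 − b²)].
- Crude test: t = r√[(n − 2)/(1 − r²)] on n − 2 degrees of freedom. At n = 30 the critical |r| is 0.361.
- Adjusted test: the same form with the partial correlation and n − 3 degrees of freedom.

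**Case 1: FA has no link to outcome beyond volume.** Then r = ab and the partial correlation is 0. Share of simulated studies with a significant result:

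| a = b | crude r = ab | crude test, n = 30 | crude test, n = 25 | adjusted test |
|---|---|---|---|---|
| 0.3 | 0.09 | 8% | 7% | about 5% |
| 0.4 | 0.16 | 13% | 12% | about 5% |
| 0.5 | 0.25 | 27% | 23% | about 5% |
| 0.6 | 0.36 | 51% | 44% | about 5% |
| 0.7 | 0.49 | 81% | 73% | about 5% |

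A Fisher-z approximation at n = 30 gives 8%, 13%, 26%, 50% and 80% for the crude test, in agreement.

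**Case 2: FA does carry extra information (n = 30).**

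| FA-outcome r | volume-outcome b | FA-volume a | partial correlation | crude power | adjusted power |
|---|---|---|---|---|---|
| 0.4 | 0.5 | 0 | 0.46 | 61% | 74% |
| 0.4 | 0.5 | 0.3 | 0.30 | 61% | 36% |
| 0.4 | 0.5 | 0.5 | 0.20 | 61% | 18% |
| 0.4 | 0.5 | 0.6 | 0.14 | 61% | 12% |
| 0.5 | 0.6 | 0.6 | 0.22 | 83% | 21% |

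For a = 0.5 in the first set: (0.40 − 0.25)/√(0.75 × 0.75) = 0.15/0.75 = 0.20. Power falls mainly because the part of the association that is separate from volume is smaller. The lost degree of freedom matters little: for a fixed partial correlation of 0.5, power moves from about 81% to 80%.

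**The case against.** The strongest reply is that no stated hypothesis is left untested. The Aim is association and interaction, Hypothesis B compares combined with individual biomarkers, and nowhere does the protocol claim that DTI adds to infarct volume. A crude correlation is a proper answer to whether a marker is associated with outcome. That stands, and it limits the point to added information and to the tract-specific reading.

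Four stronger readings are tempting, and the documents do not support them.

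- A reader might take 27%, 51% and 81% as false-positive rates of the planned test. They are not. In those scenarios FA and outcome truly correlate at 0.25, 0.36 and 0.49, and the test detects a real crude association. At links of 0.3 to 0.4 the figures are only 8% to 13%.
- A reader might treat the list as closed and conclude that an adjusted result could not be reported. The text never says that only these analyses will be done, two objectives refer to brain biomarkers in general terms, the data are collected, and an analysis plan that is not shown may add to the list.
- A reader might conclude that any claim for DTI must rest on the adjusted estimate. Case 2 shows why not: with a genuine added effect, adjusted power can be 12% to 36%, so a null result would often be uninformative. Tract damage may also be part of how a larger infarct worsens function, so the adjusted figure does not supersede the crude one.
- A reader might foresee a successor algorithm built on a marker without value. The protocol uses this early observational study to inform the design and size of a confirmatory study, and adopts no algorithm from these correlations.

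The comparator and the paired reporting survive all of this, because they take nothing away from the crude analyses.

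**Conclusion.** The point holds in limited form. Infarct volume is collected but unused in the listed analyses, so they cannot show whether corticospinal DTI is informative beyond infarct size. This is not simply detail left for later, because the protocol itself names the covariate in Analysis A and the contents of the final regression. The crude results are not invalid.

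The size depends on two correlations that the protocol does not give. If both are below about 0.4 the issue is minor. From about 0.6 upwards, a significant crude correlation would be found in half or more of studies of 30 patients even if FA added nothing to volume. Without infarct volume in the analysis, readers cannot tell which situation applies. For an exploratory study of 30 patients this is a moderate weakness that is cheap to repair.

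**What to change.** In Data analysis:

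1. Add infarct volume, log-transformed if skewed, as a named individual brain imaging biomarker in the correlations with 3-month Fugl-Meyer score, motor NIHSS and dynamometry, as the conventional-MRI comparator for DTI.
2. As a secondary or sensitivity analysis, report the FA coefficient or partial correlation for Fugl-Meyer with a 95% CI, both without and with infarct volume.
3. Limit any statement that DTI adds information beyond infarct size to what the two estimates together support. Set no rule that depends on significance of the adjusted estimate.

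The cost is wording, with no new measurement or visit. Statistically it is one degree of freedom and, if FA and volume are strongly related, a less precise and often inconclusive adjusted estimate. Showing both estimates makes that visible. Analysis A already carries sarcopenia measures, so at this sample size infarct volume should be the only further covariate added for this purpose.

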# Study withdrawal

No specific study withdrawal criteria have been set. Participants may withdraw from the study at any time for any reason. Should a patient decide to withdraw from the study, a reason for withdrawal will be sought but patients can choose to withdraw without providing an explanation. If a participant decides to withdraw it will not affect the normal care they receive. Data collected prior to withdrawal will be used in the study analysis unless consent for this is specifically withdrawn.

SINONIMS Protocol V1.0 24.09.18 (Amendment 1.1 01/11/19) (Amendment 1.2 17/08/20) (Amendment 1.3 05/01/21) (Amendment 1.4 18/05/2021) IRAS ID 249942 Page 14 of 24

Clinical teams, investigators or other members of research team may also withdraw participants from the study at any time if they feel it is no longer in their interest to continue, for example, because of inter-current illness.

# Safety

MRI is already used in clinical practice with known risks which are minimised by a detailed MRI safety screening process. All study participants will be routinely screened with a standard MRI safety questionnaire before undergoing the study as detailed before (Please see Planned Advance MRI section). All patients with a contra-indication to MRI will be excluded from the study. The MRI study does not involve injection of any contrast agent.

As this is a blinded observational study without any change in patient care, standard adverse event reporting will not be completed.

Should a medical event occur which is serious and unexpected (results in death; is life-threatening; requires inpatient hospitalisation or prolongation of existing hospitalisation; results in persistent or significant disability or incapacity; consists of a congenital anomaly or birth defect; otherwise considered significant by investigator) and is perceived to be possibly or definitely related to a study intervention (for e.g. MRI imaging), a separate study Serious Adverse Event form will be completed. All such events will be reported to the principal investigator, study sponsor and Research Ethics Committee. Checking for SAE will take place at the time of the baseline and 3 month assessments.

All the MRI studies undertaken as part of the study will be reviewed by a Consultant Radiologist. If there is a significant unexpected finding on MRI, the PI will be informed who will then communicate to this to the hospital team, the GP and the patient on a case by case basis.

All deaths of study participants will be recorded.

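### The SAE form and the sponsor report are limited to unexpected events, with no definition of unexpected, so a non-fatal serious event related to a study procedure but judged expected could get neither

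*Protocol*

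**What the plan says.** All the reporting rules are in the protocol's Safety section.

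- On the procedure: "MRI is already used in clinical practice with known risks which are minimised by a detailed MRI safety screening process". No individual risk is listed.
- On routine collection: "standard adverse event reporting will not be completed". The reason given is that the study is observational and does not alter care.
- On the SAE trigger: "Should a medical event occur which is serious and unexpected", followed by a bracket of seriousness criteria, then "and is perceived to be possibly or definitely related to a study intervention". When these are met, "a separate study Serious Adverse Event form will be completed".
- On recipients: "All such events will be reported to the principal investigator, study sponsor and Research Ethics Committee".
- SAEs are looked for at the baseline and 3-month assessments, and every participant death is to be recorded.

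The bracket after the opening words of the trigger defines seriousness only. Neither that section nor any other defines unexpected or lists expected events.

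**The concern.** Expectedness is often used to decide which serious events need a further report to an outside body. Here it is placed earlier and decides whether the event is written down as an SAE at all. Because ordinary adverse events are not collected either, an event that fails the expectedness test has no second place to be recorded.

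The section first acknowledges that MRI has known risks and then asks for a form only when the event is unexpected. An assessor who takes a known risk to be an expected one could complete no form and still be following the protocol. Another assessor could treat the same injury as unexpected and report it. Nothing in the text settles which is right.

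The population makes this more than a drafting point. Participants are scanned 1 to 4 weeks after a stroke with a leg deficit. Study population allows people who need help to transfer, including by hoist at one of the two scanning sites. Appendix 7 has patients repositioned between the brain and thigh scans. Foreseeable harm around the scan is the kind a sponsor would want to hear about.

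**Working it through.** No arithmetic applies, and the plan states no figure on this point. The check is to read the rule as a logical condition and then look for any other route that would catch what it leaves out.

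**Step 1: the rule.** Serious AND unexpected AND possibly or definitely related → SAE form → principal investigator, sponsor and Research Ethics Committee. If any one part fails, the stated rule requires no form. The recipients sentence covers only events that passed all three parts.

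**Step 2: apply it by type of event.**

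| Event | SAE form | Stated report to sponsor | Other record |
|---|---|---|---|
| Serious, related, unexpected | Yes | Yes | Not needed |
| Serious, related, judged expected, non-fatal | No | No | None stated |
| Fatal, related, judged expected | No | No | Death recorded |
| Serious, unrelated | No | No | Only if fatal |

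The second row is the gap. The third row is a partial gap: the death is recorded, but no recipient is named.

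**Step 3: look for another route for the second row.**

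- *SAE checks at baseline and 3 months (Safety).* The sentence does not repeat the expectedness condition, but it sets when to look. The only stated rule for completing a form still contains that condition.
- *The last seriousness criterion (Safety).* It lets the investigator call other significant events serious. That widens seriousness and leaves expectedness in place.
- *Radiologist review (Safety).* This deals with unexpected findings on the images, not with injury.
- *Cancelled scans (Planned advanced MRI imaging).* Scans cancelled for a safety concern are documented and reported. Harm during a scan that went ahead is not covered.
- *Patients who cannot tolerate or complete the scan (Case ascertainment, consent and recruitment).* They stay in the feasibility analysis, but no record of harm is specified.
- *Withdrawals (Study withdrawal).* A reason is sought, but the patient need not give one, and an injured participant need not withdraw.

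None of these amounts to a record of, or a sponsor report for, a non-fatal, serious, related event judged expected. Appendix 1 (study processes) is an attachment that is not reproduced, so it could not be checked.

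**Step 4: does the text itself class any MRI harm as expected?** No. It speaks of known risks as a class, gives no list and defines no term. The gap therefore opens when an assessor judges an event expected, which the text permits but does not require.

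**The case against.** The strongest reply is that the rule may lose nothing in practice. Participants pass repeated MRI safety screening, those with contra-indications are excluded, and no contrast agent is given. On that footing no serious MRI injury is expected in any participant, so any that occurred would be unexpected and would be reported in full. A risk known for MRI in general is not the same as a serious event expected in a screened individual. The protocol also gives a reason for light reporting, and whether a related-and-unexpected trigger falls short of an outside governance standard cannot be settled from this document.

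Much of this stands. A reader might infer that harm from a known risk is by definition expected, so that the rule captures none of it. The documents do not support that, because they neither define expectedness nor name any risk. Nor can it be said that nothing is recorded: deaths are, and the routes in step 3 leave partial traces.

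A reader might also infer that the feasibility conclusions or the later study would rest on a false safety record. The Objectives section does not go that far. It measures feasibility by "description of recruitment rate, drop-out rate and rate of incomplete and sub-optimal imaging", and safety is not among its aims. For the same reason a confidence limit for zero events in 30 patients is beside the point: the protocol sets out to estimate no safety rate.

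What the reply does not remove is the dependence on an undefined word. The favourable reading is reasonable, but so is the other one, and the protocol has no fallback if an assessor adopts it.

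**Conclusion.** The point holds in a limited form. The Safety section makes expectedness a condition for the SAE form and for telling the principal investigator and sponsor, leaves the term undefined, and waives the collection that would otherwise provide a fallback. A non-fatal serious event related to a study procedure and classed as expected could therefore go without a form or a sponsor report.

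The size is one class of event, not a percentage. Few such events are likely in 30 patients, and the protocol gives nothing from which to calculate how many. The conclusion assumes that an assessor could reasonably call some MRI-related or transfer-related harm expected, and that the Appendix 1 attachment adds no further reporting route. It does not depend on any outside reporting standard. This is an inexpensive correction to a stated rule and casts no doubt on the study's planned analyses.

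**What to change.** In the Safety section:

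1. Remove the expectedness condition from the trigger for the SAE form and from notification of the principal investigator and sponsor. Every serious event judged possibly or definitely related to a study procedure is then recorded and notified.
2. Keep expectedness only as the condition for the report to the Research Ethics Committee, and define it there.
3. State that all related serious events, expected or not, will be reported with the study results.

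The cost is a few sentences in one section and at most a few extra forms in 30 patients. The seriousness criteria, the relatedness condition, the waiver of ordinary adverse event reporting and the timing of the SAE checks can stay as they are. Patient care and study visits do not change.
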